Data analysis: For aims 1, statistical analyses to address baseline comparison: Subjects' baseline characteristics (demographics and medical conditions) will be compared between the intervention and control groups using 2-sample t-tests (or appropriate nonparametric tests if the assumption of normality appears to be violated) and chi-square tests for continuous and categorical variables. Descriptive statistics will be used (means, frequencies, standard deviations, 95% confidence intervals) for all variables. We will examine the Aim #1a outcomes using a Poisson mixed-effects model to account for the nesting of outcomes within centers. We will account for baseline measures of resident activation and health status and resident demographics to statistically adjust for baseline imbalances, reduce residual intra-cluster correlation and improve the precision of estimated effects. Power analyses were performed via a simulation study in R version 3.4. and the lme4 package. We used 3 months of pilot data to guide and set assumptions for the data generating process. Based off initial data, we assumed centers ranged in size from 25-45 participants, and that roughly 30% of participants at each site would consent to the trial. Of those who consent, 50% will be randomized to the intervention. We fit the pilot data to a Poisson mixed effects model to obtain an estimate of the average monthly fall rate (0.49) as well as the between cluster variation in log fall rate ( $\sigma_{\text{twn}} = 0.467$ ). We generated 1000 sample data sets assuming different effect sizes (40%, 30%, 25% reduction in falls) and calculated the power obtained to detect this improvement due to intervention, as a function of the number of centers.

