Following the sample size for a time-averaged response methodology laid out in Fitzmaurice et al., we adjusted the total number of centers needed by a factor related to the number of observed months, anticipated participants per center (30% of 35 participants per center with 10% dropout) and the correlation between measurement months. The dropout rate was roughly at ~1% per month so a 10% dropout over 6 months is a conservative estimate. We assumed an extremely conservative estimate of the correlation between time points (months) of 0.8 and 6 months of follow-up. Reproducible R code is available at <https://github.com/[name]/>. We estimate that a total sample size of 460 ( $n=230/\text{arm}$ ) out of 19 facilities will be needed for a power of 80% to detect a 30% reduction in falls in the intervention group vs. control. Our approach of focusing on estimation and uncertainty and accepting the sample size collected for the main study, is congruent with experts' recommendations stating that the purpose of economic evaluation is not hypothesis testing; given there is no hypothesis testing, there is no requirement for a separate sample size calculation. For Aim 2, we will use similar descriptive statistics as described in Aim 1. For Aim 3, We will use a multivariate regression model to examine predictors of the main outcome, ER visits and hospitalizations (binary variable), using time to fall discovery by staff and time spent on the ground as the main predictors while controlling for baseline participant characteristics and facility characteristics.

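### The claim of 80% power at a month-to-month correlation of 0.8 is unsupported: the stated simulation inputs leave out the between-resident variance that such a correlation requires

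*Combined protocol and SAP*

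**What the plan says.** The Data analysis text under Clinical outcomes plans the Aim 1 comparison with a "Poisson mixed-effects model to account for the nesting of outcomes within centers". Its power simulation takes two quantities from a Poisson mixed model fitted to 3 months of pilot data. The model was used "to obtain an estimate of the average monthly fall rate (0.49) as well as the between cluster variation in log fall rate", the latter being 0.467. Data sets were generated for several effect sizes, and the authors "calculated the power obtained to detect this improvement due to intervention, as a function of the number of centers".

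The number of centres was then adjusted with a time-averaged-response method, using the number of months, the expected residents per centre with 10% dropout, and the correlation between months: "We assumed an extremely conservative estimate of the correlation between time points (months) of 0.8 and 6 months of follow-up". The result is 460 residents (230 per arm) in 19 facilities, which "will be needed for a power of 80% to detect a 30% reduction in falls in the intervention group vs. control".

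No between-resident variance, overdispersion parameter or alpha is stated. The R code is cited by link and is not part of the documents.

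**The concern.** The time-averaged factor for m months, [1 + (m − 1)ρ]/m, multiplies the total variance of one month's response. That total must already contain the resident-to-resident variation that makes a resident's months correlate. If counts are Poisson around each resident's own rate, a correlation of ρ implies a single-month variance of mean/(1 − ρ), not the mean. Using a high ρ in the factor together with a variance that has no resident component counts the correlation but not its source.

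At stake is the robustness of the randomised comparison. The plan presents 0.8 as a wide safety margin. If that margin is absent, a true 30% reduction could be missed at correlations that the plan says it covers, and a null result could be given more weight than it deserves.

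**Working it through.** **Inputs from the Data analysis text:** monthly fall rate 0.49; between-centre SD of log rate 0.467; rate ratio 0.70; power 80%; 6 months; ρ = 0.8; 1:1 allocation; 230 per arm. **Assumed:** alpha 0.05 two-sided (not stated); no resident-level term in the code.

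**1. Reproduce the plan's 460.** Read 0.49 as the rate of the median centre. The mean over centres is then 0.49 × exp(0.467²/2) = 0.5465.
- Variance sum for one month, Poisson only: 1/0.5465 + 1/(0.7 × 0.5465) = 4.444.
- Single-month size: (1.96 + 0.8416)² × 4.444 / (ln 0.7)² = 274.2 per arm.
- Time-averaged factor: (1 + 5 × 0.8)/6 = 0.833.
- 274.2 × 0.833 = 228.5 per arm, 457 in total, against the stated 460.

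A simulation of one month with centres of 25–45 and 30% consent gave 80.5% power at 546 residents, and 546 × 5/6 = 455. So 460 is recovered with no resident-level variance and no dropout inflation. Other readings do not recover it: 0.49 taken as the overall mean gives 510, adding dropout to the matching version gives 508, and one-sided 5% gives 360–446.

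**2. Correlation implied by the stated variance.** The centre-level variance of the monthly rate is 0.5465² × (exp(0.467²) − 1) = 0.2986 × 0.2437 = 0.0728. The implied correlation between months is 0.0728/(0.0728 + 0.5465) = 0.12. The inputs cannot generate 0.8.

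**3. A consistent factor.** With single-month variance mean/(1 − ρ), the factor becomes [1 + 5ρ]/[6(1 − ρ)] = 1/6 + ρ/(1 − ρ). At ρ = 0.8 this is 4.167 instead of 0.833, a ratio of 1/(1 − 0.8) = 5.

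**4. Power at 230 per arm.** Power = Φ(|ln 0.7|/√(V/230) − 1.96), where V is the per-resident variance sum for the log rate ratio. Example at ρ = 0.8: V = 4.444 × 4.167 = 18.52, √(18.52/230) = 0.2838, 0.3567/0.2838 = 1.257, and Φ(1.257 − 1.96) = 24%.

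Three resident models were used, each at both readings of 0.49:
- *Equal ρ in both arms:* V = (1/μ + 1/(0.7μ)) × [1/6 + ρ/(1 − ρ)].
- *Common frailty variance:* τ² = ρ/[(1 − ρ)μ], V = 2τ² + 1/(6μ) + 1/(4.2μ), with ρ taken in the control arm.
- *Lognormal resident intercept fitted by likelihood:* same τ², V from the numerically integrated Fisher information.

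| Model | Mean rate μ | ρ = 0.2 | 0.3 | 0.4 | 0.5 | 0.6 | 0.8 | 80% kept up to ρ ≈ |
|---|---|---|---|---|---|---|---|---|
| Marginal, equal ρ | 0.49 | 96% | 88% | 76% | 61% | 47% | 22% | 0.37 |
| Marginal, equal ρ | 0.5465 | 98% | 91% | 80% | 66% | 51% | 24% | 0.40 |
| Marginal, common frailty | 0.49 | 98% | 92% | 82% | 69% | 54% | 26% | 0.42 |
| Marginal, common frailty | 0.5465 | 99% | 95% | 86% | 73% | 58% | 28% | 0.45 |
| Lognormal intercept | 0.49 | 98% | 94% | 88% | 81% | 73% | 54% | 0.51 |
| Lognormal intercept | 0.5465 | 99% | 96% | 91% | 84% | 76% | 57% | 0.55 |

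With 10% dropout, 207 complete per arm. Power at 0.8 is then 20–26% on the marginal analyses and 50–52% with the lognormal intercept, and the lowest threshold falls from 0.37 to 0.34.

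**The case against.** The strongest reply is that the simulation code is not in the documents. The plan names two quantities taken from the pilot fit but does not say that they were the only variance terms simulated. The match to 460 also depends on choices: 0.49 as a median-centre rate, two-sided 5%, and no dropout, although the plan says that dropout was allowed for. Nor does it recover the 19 facilities: at 30% of 35 = 10.5 residents each, 19 facilities give about 200 residents, and 460 would need about 44. This stands. The missing resident term is an inference, well supported by the text and the arithmetic but not proven.

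A second reply is that no single number describes the shortfall. This also stands. The result depends on the resident model, and on whether 0.8 is meant within centres or overall. If it is overall and centre and resident effects multiply, the marginal figures at 0.8 rise to 29–34% and the thresholds to 0.49–0.53 (μ = 0.5465). The planned baseline adjustment may also recover some precision, but the plan puts no figure on it.

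Third, 0.8 was chosen as an upper bound, not as an expected value, and at 0.2–0.3 the design is well powered. This limits the consequence but does not rescue the claim: the plan says that the bound is covered, and under every resident model examined it is not.

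A reader might go further and infer that the trial has about 24% power, that 460 residents are too few, or that 0.40 is the exact limit of what the design covers. The documents support none of these. They give no estimate of the true month-to-month correlation, and both 24% and 0.40 belong to one of several defensible models.

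**Conclusion.** The concern holds as an inconsistency between the stated variance inputs and the stated correlation. No printed sum is wrong, and 460 may well be adequate. What fails is the assurance of "a power of 80% to detect a 30% reduction in falls" at a correlation of 0.8. On the stated inputs, power there is roughly 22–28% on a marginal analysis, and about 50–57% with a lognormal resident intercept (the lower end allowing for dropout). Power of 80% is kept up to a correlation of somewhere between about 0.37 and 0.55 at 230 per arm.

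These figures assume two-sided 5%, valid standard errors, and no resident-level term in the code. The fivefold gap in single-month variance at 0.8 does not depend on alpha, fall rate or effect size; it needs only Poisson counts around each resident's own rate. If the code does contain a resident-level variance, the plan should state it, and the power would need to be judged on that value.

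**What to change.** - Estimate the between-resident variance of the fall rate from the 3 months of pilot data already held, and report it beside the between-centre SD.
- Add that variance, and the stated 10% dropout, to the data-generating step of the simulation.
- In the sample-size text, state alpha and sidedness, say whether 0.49 is a median-centre or an overall mean rate, and say whether the correlation is within centres or overall.
- Report power at 230 per arm over a range of correlations, for example 0.2 to 0.8, taken from the re-run. Do not write in a single threshold such as 0.40.
- Remove the statement that 80% power holds at 0.8 and the description of that value as very conservative.

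The cost is a re-run of existing code and a reworded paragraph. Enrolment does not change. The downside is that the stated power will look less favourable.

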## **AIMS & HYPOTHESES FOR RANDOMIZED, WAITLIST-CONTROL STUDY.**

**Aim #1. To assess whether SafelyYou Guardian + HIL will lower fall rates.** Hypothesis 1. Compared to standard-of-care (waitlist control group), SafelyYou Guardian will reduce fall rates in study participant over the study period of 6 months.

**Aim #2. To assess how use of the SafelyYou Guardian affects time spent on the ground after a fall.** Longer time to fall discovery is associated with higher human suffering and often leads to higher medical morbidity/mortality. Hypothesis 2: SafelyYou Guardian + HIL will reduce time to fall discovery (time from fall to staff notification) to under 5 minutes and reduce time spent on the ground to under 15 minutes. Since there is no way to measure control participants time spend on the ground, the aim will not have a comparison but will be descriptive.

**Aim #3. To assess whether SafelyYou Guardian will lead to improvement in hard clinical outcomes.** Hypothesis 3: SafelyYou Guardian participants will lower ED visits and hospitalizations when compared to control. This reduction in ED and hospitalization will correlate with reduced fall rates (aim #1) and reduced time spent on the ground (aim #2). We will review the strength of the association with aim #1 and #2 outcomes.

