### Design

For Aim 1, we plan to recruit 460 study participants from 19 memory care facilities. For the purpose of this study, facilities will include Skilled Nursing Facilities (SNFs), or equivalent. Aim 1 will be a randomized controlled study using a waitlist control group. The randomization will occur at the individual (resident) level within each facility to control for variations at each facility in terms of facility size, facility administration, and staff training. During the first 6 months, n=230 will receive the intervention (SafelyYou Guardian, i.e. real-time alarms through a phone call from the HIL to the facility, front line staff intervention, and OT review), and n=230 will not receive the intervention. This design is the most rigorous way to test the intervention against the control: the randomization allows for control of confounding variables and has been previously used in the evaluation of medications, non-pharmacological, and mobile electronic interventions (where use of placebo treatment and blinding is not feasible) [87-89]. Previous work used a baseline as control, allowing possible confounding variables. As we recognize that 50% of the interested participants will not receive the intervention, those residents will be offered the intervention for a 6-month extension period (in order to accomplish Aim 2). This is the best compromise between the need for a rigorous randomized controlled trial vs. ethical responsibility to maximize benefit to each study participant.

For Aim #2, we will measure response times to each fall and the amount of time a resident spends on the ground after each fall. We intend to include all 460 participants' data from Aim #1. These will be participants who receive the initial intervention (n=230) and the additional participants who are on the waitlist control group who will receive the intervention in the second 6month period. The design for Aim #2 is observational in nature. The significance is that a large cohort of video data about the naturalistic progression of falls in residents with dementia has never been conducted to our knowledge. We will determine if the two time variables (time to fall discovery by staff and time spent on the ground after a fall, controlling

for baseline participant characteristics – i.e., demographics and medical conditions) and facility size, will predict need for ER visits or hospitalizations.

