For aim #3, we will ascertain the occurrence of fall in the intervention group by doing follow-up case review of each detected fall. For the control group, we perform biweekly check with facility staff and family regarding knowledge and documentation of any falls. For falls in both the intervention and control group, we will additional collected data regarding occurrence of ED visit and hospitalization days. We will also include occurrence (or absence) of any operations, intensive care unit stays, and other medical procedures. We will also collect mortality data.

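### Aims 2 and 3 state no unit of analysis and no method for repeated falls within residents and facilities: applied to falls as written, Aim 2 intervals would be too narrow and Aim 3 inference may be anti-conservative

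*Combined protocol and SAP*

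**What the plan says.** The Design section makes the fall the unit of measurement for Aim 2: "we will measure response times to each fall and the amount of time a resident spends on the ground after each fall". For Aim 3 the same section attaches the clinical outcomes to falls in both groups: "we will additional collected data regarding occurrence of ED visit and hospitalization days".

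The methods are in the Data analysis paragraphs under Clinical outcomes. Aim 1 has a Poisson mixed-effects model for nesting within centers. For Aim 2 the text is "For Aim 2, we will use similar descriptive statistics as described in Aim 1", and the Aim 1 wording it points to is "Descriptive statistics will be used (means, frequencies, standard deviations, 95% confidence intervals) for all variables". The Aim 3 method reads "We will use a multivariate regression model to examine predictors of the main outcome, ER visits and hospitalizations (binary variable". Its principal explanatory variables are the two times from Aim 2, and the only provision for differences between residents or facilities is covariate adjustment, worded as "while controlling for baseline participant characteristics and facility characteristics".

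For Aims 2 and 3 the plan names no random effect, GEE, robust variance or bootstrap, and no unit of analysis. The Aim 3 outcome is binary in this text, but the outcome description under Clinical outcomes refers to numbers of ER visits and hospitalizations.

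**The concern.** Falls by one resident share that resident's condition and habits, and falls in one facility share its staff and transfer practice. The plan recognises facility variation: it randomizes within facility and fits a mixed model for Aim 1. Within-facility randomization does not help Aims 2 and 3, because Aim 2 is observational and the times exist only for monitored residents.

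Ordinary intervals and ordinary regression assume independent observations. Two results are at stake. One is the precision claimed for the Aim 2 times, which Hypothesis 2 sets against targets of under 5 and under 15 minutes. The other is which Aim 3 predictors of ER visit or hospitalization are called significant.

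**Working it through.** **The plan's own figure.** The plan gives no figure for Aim 2 or 3. Its Aim 1 total of 460 can be reproduced, which supports taking the fall rate from the same paragraph.
- Inputs from Data analysis: monthly rate 0.49, between-center SD of log rate 0.467, 30% reduction, power 80%, month-to-month correlation 0.8, 6 months. Two-sided alpha 0.05 is assumed; the documents do not state it.
- Marginal rate r = 0.49 × exp(0.467²/2) = 0.5465. Time factor = (1 + 5 × 0.8)/6 = 0.833.
- n per arm = (1.960 + 0.842)²/ln(0.7)² × (1/r + 1/(0.7r)) × 0.833 = 228.5, a total of 457 against 460.

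**Step 1: number of falls.** With 460 residents, 19 facilities and 6 monitored months each:
- no effect: 460 × 0.49 × 6 = 1,352 falls, or 2.94 per resident and 71 per facility;
- 30% reduction: 1,352 × 0.7 = 947 falls, or 2.06 per resident and 49.8 per facility.

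The power text also gives 30% of 35 = 10.5 residents per center, or 9.45 after 10% dropout. That conflicts with 460/19 = 24.2, so both sizes are carried forward. At 0.343 × 6 = 2.058 falls per resident, they give 21.6 and 19.4 falls per facility.

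**Step 2: Aim 2 intervals, facility level only.** Design effect (DE) = 1 + (m − 1) × ICC, where m is falls per facility. The interval is too narrow by a factor of √DE. Cells show DE and √DE; all ICCs are assumptions.

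| Facility ICC | m = 49.8 | m = 21.6 | m = 19.4 |
|---|---|---|---|
| 0.02 | 1.98; 1.41 | 1.41; 1.19 | 1.37; 1.17 |
| 0.05 | 3.44; 1.86 | 2.03; 1.42 | 1.92; 1.39 |
| 0.10 | 5.88; 2.43 | 3.06; 1.75 | 2.84; 1.69 |

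**Step 3: resident and facility levels together.** DE = 1 + (2.058 − 1) × ICC_res + (49.8 − 1) × ICC_fac. The true coverage of a nominal 95% interval is 2Φ(1.96/√DE) − 1.

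| ICC_res / ICC_fac | DE | √DE | Coverage |
|---|---|---|---|
| 0.05 / 0.01 | 1.54 | 1.24 | 89% |
| 0.10 / 0.02 | 2.08 | 1.44 | 83% |
| 0.20 / 0.05 | 3.65 | 1.91 | 70% |
| 0.30 / 0.10 | 6.20 | 2.49 | 57% |

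These figures assume equal clusters. Letting facility fall rates vary with the plan's SD of 0.467, with and without added variation between residents, raises DE to between 1.8 and 9.7 over the same ICC pairs at the reduced fall rate.

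**Step 4: one record per resident instead.** Only facility clustering remains: DE = 1 + (24.2 − 1) × ICC = 1.23 at ICC 0.01 and 3.32 at 0.10. Intervals are then 1.11 to 1.82 times too narrow.

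**Step 5: Aim 3.** Fall-level logistic regression was simulated with 1,500 runs per scenario, an assumed event risk of about 20%, no true effect and nominal 5% tests. Monte Carlo standard error at 5% is √(0.05 × 0.95/1500) = 0.6 percentage points.

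| Term tested | Type I error |
|---|---|
| Time predictor with no clustering of its own, ordinary SE | 4.6–5.7% |
| Time predictor clustered (facility ICC 0.05–0.20, resident ICC 0.10–0.20), ordinary SE | 6.7–17.1% |
| Resident-level covariate, ordinary SE | 8–20% |
| Facility-level covariate, ordinary SE | 15–40% |
| Time predictor, facility-clustered SE with t on 18 df | 5.0–7.7% |

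**The case against.** The strongest reply is that the plan never says falls will be treated as independent. The unit of analysis is open, and the count wording for Aim 3 leaves room for a resident-level analysis. Aim 2 is explicitly non-comparative: "the aim will not have a comparison but will be descriptive". The 95% interval wording reaches it only by cross-reference from text on Aim 1. Aim 3 adjusts for facility characteristics, which can absorb some between-facility correlation. Discovery time runs partly through the detection system and the remote reviewer, who is not facility staff, so its facility ICC may be small. About 50 falls per facility is a product of the plan's inputs, not a figure the plan states. It ignores dropout and the fact that cameras are in bedrooms only.

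Much of this stands. A reader might infer that the plan declares independence, that Aim 2 p-values are affected, or that response time is known to depend strongly on staffing. The documents support none of these. A reader might also infer that the Aim 3 time predictors will be called significant too often. That follows only if the times themselves cluster.

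The gap remains. The same paragraph names a clustering method for Aim 1 and only ordinary methods for Aims 2 and 3. The one facility characteristic named in the Design section's account of this prediction is size; fixed covariates do not remove residual facility correlation or correlation among one resident's falls. A resident-level analysis still leaves facility clustering, and 19 to 22 falls per facility still gives design effects of about 1.4 to 3.1.

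**Conclusion.** The concern holds as a gap in specification with a predictable direction. If the stated methods are applied to falls, Aim 2 intervals are too narrow under any positive correlation. The likely factor is 1.4 to 2.4 at about 50 falls per facility, and 1.2 to 1.75 at 19 to 22. Aim 3 inference may be anti-conservative, from no inflation to about 17% for the time predictors, with 8–20% for resident-level and 15–40% for facility-level covariates.

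The sizes rest on assumed ICCs, an assumed event risk and fall counts derived from pilot inputs. The direction for Aim 2 does not depend on their exact values. Aim 2 point estimates are little affected. It would be wrong to read this as undermining the trial's main result: the primary Aim 1 analysis has its own mixed model and is outside this point. The correction should be made before the data are analysed, but it is not a reason to change the design.

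**What to change.** 1. State the unit of analysis for Aims 2 and 3, and reconcile the binary and count descriptions of the Aim 3 outcome.
2. For a fall-level Aim 3 model, prespecify a logistic mixed model with resident and facility random effects. The alternative is GEE or logistic regression with facility-clustered standard errors and a small-sample correction for 19 facilities. The 7.7% upper figure with t on 18 df shows that the choice of correction should be written down. For a resident-level model, keep the facility term.
3. Compute every Aim 2 95% interval with facility-clustered variance (t, 18 df) or a bootstrap that resamples facilities.
4. Report the estimated facility and resident ICCs, since the plan has none.

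The cost is a few sentences in the plan, a few lines of code and wider intervals. No further data or participants are needed.
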